- Dose regimen: once daily.

Noninvestigational medicinal products

A radiological, signal-enhancing, intravenous (IV) contrast medium will be used for T1-contrast-enhanced MRI sequences. A locally approved contrast agent will be used.

Due to a potential safety risk related to gadolinium (Gd) deposition in the brain seen with certain contrast agents, these agents should be used in accordance with local recommendations and regulations. Otherwise, use of these agents will be similar to their routine use and will be sourced locally. The study manual will provide more details describing their administration in this trial.

Continued access to intervention after the end of the study

After the end of this study, participants who successfully complete the trial on SAR442168 may be offered the option to participate in a Phase 3 long-term safety (LTS) study for up to an additional 3 years, or until SAR442168 is approved in their respective country, whichever comes first. Details of the Phase 3 LTS study will be described in a separate protocol. If this program is terminated earlier, other available RMS treatments will need to be considered at the discretion of the treating physician.

Statistical considerations:

No statistical comparisons between treatment groups will be made. Summaries using descriptive statistics will be provided by visit for parameters.

Sample size calculations:

There are no sample size calculations for this long-term extension study. Sample size will be based on the elective participation of participants who complete the DRI15928 study, meet the eligibility criteria, and enroll in this LTS16004 study.

Primary analysis:

The safety of long-term SAR442168 treatment will be evaluated using descriptive statistics, summarizing incidence of adverse events (Aes), serious adverse events (SAEs), and clinically significant abnormalities (PCSAs) for clinical laboratory tests, and summarizing safety findings on MRI, electrocardiogram (ECG), and vital signs parameters by visit.

Analysis of secondary endpoints:

[figure not shown]
Summaries using descriptive statistics will be provided by visit.

Independent Hepatology Assessment Committee: Yes

Data Monitoring Committee: Yes

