1.3 SCHEDULE OF ACTIVITIES (SOA)

In this clinical study, a month is considered to be a period of 4 weeks (28 days).

Table 1 - A - Schedule of activities (up to Year 1)

Procedure	Screening	Baseline/start of IMP	Intervention Phase					Premature End of Treatment ^b	
			M1	M3	M6	M9	M12		
Month (a window of ± 7 days is allowed for all visits after screening)	W-6 to D1^a	D1^a							
Informed consent	X							If switch to Part B	
Visit at clinical site ^c	X	X	X	X	X	X	X	X	X
Inclusion/exclusion criteria	X								
Prior/concomitant medications	X	X	X	X	X	X	X	X	X
Study IMP Administration									
SAR442168 (dispensation and accountability)		X	X	X	X	X	X	If switch to Part B	X (Accountability only)
Safety^c									
Physical examination ^{d, e}	X	X	X	X	X	X	X	X	X
Height	X								
Body weight	X	X	X	X	X	X	X	If needed	X
Vital signs ^e	X	X	X	X	X	X	X	X	X
12-lead ECG ^e	X	X	X	X	X	X	X	If needed	X
Hematology, biochemistry ^{e, f}	X ^g	X ^g	X	X	X	X	X	If needed	X
Urinalysis ^{e, f}	X ^g	X ^g	X	X	X	X	X	If needed	X
β -HCG test (if applicable) ^h	X	X	X	X	X	X	X	If needed	
Serum FSH (if applicable) ⁱ	X								
Suicidality assessment (C-SSRS)	X	X	X	X	X	X	X	If needed	X

Procedure	Screening	Baseline/start of IMP	Intervention Phase					Premature End of Treatment ^b	
			M1	M3	M6	M9	M12		
Month (a window of ± 7 days is allowed for all visits after screening)	W-6 to D1^a	D1^a						UN SCH^b	
Adverse event collection	<----->								
Efficacy									
EDSS		X ^j		X	X	X	X	If MS relapse suspected	X
MRI ^o		X ^j		X	X		X	If needed	X
		X	X	X	X	X	X		
Pharmacokinetics									
SAR442168 pharmacokinetic plasma samples								If MS relapse suspected or in case of index AEs	X ^p
Pharmacodynamics / Biomarkers									
Exploratory biomarkers: [REDACTED]		X ^l						If MS relapse suspected or in case of index AEs	X
Exploratory biomarker plasma samples [REDACTED]		X		X	X		X		X

Abbreviations: AE: adverse event; β -HCG: beta human chorionic gonadotropin; BTK: Bruton's tyrosine kinase; C-SSRS: Columbia Suicide Severity Rating Scale; [REDACTED] D: day; ECG: electrocardiogram; EDSS: Expanded Disability Status Scale; FSH: follicle-stimulating hormone; IMP: investigational medicinal product; M: month; MRI: magnetic resonance imaging; MS: multiple sclerosis; [REDACTED]; [REDACTED] UNSCH: unscheduled; W: week. Note: All assessments shall be done as designated in this SoA unless not permitted according to local regulations.

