In addition, appropriate safety monitoring measures are in place including physical examination, monitoring of vital signs and clinical labs, ECG, and collection of AEs and AESIs. Every effort will be made to complete trial visits and trial assessments and to provide study drug for participants. If needed, temporary treatment discontinuation can be considered by the Investigator or by the participant for any reason, including due to any safety concerns because of COVID-19 or another illness or if there is a need for a prohibited concomitant medication. Treatment can be resumed later when it is considered safe and appropriate.

Last, the Sponsor has updated the ICF to inform participants of the general risks for COVID-19 during the pandemic and the importance of appropriate behavioral modifications to reduce or ideally prevent exposure to the SARS-CoV-2 virus.

In conclusion, considering the mechanism of action of SAR442168, the lack of data on the COVID-19 course in MS patients receiving DMTs, the safety monitoring and mitigation measures already in place, and the favorable benefit-risk profile observed in the completed Phase 2b study in RMS patients, the Sponsor maintains that the trial can be conducted as planned.

Overall benefit: risk conclusion

No safety or tolerability concerns have been identified in the completed Phase 1 studies in healthy participants or the Phase 2b trial (DRI15928) in participants with RMS. In addition, the positive Phase 2b primary endpoint results support the potential for clinical efficacy.

Drug-induced liver injury has been identified in the ongoing Phase 3 trials. The reported events occurred in Months 1 to 3 after the start of the IMP. Exclusion criteria and monitoring frequency have been updated in all actively recruiting protocols.

The potential risks associated with SAR442168 are well defined and appropriate safety monitoring measures and risk mitigation strategies are in place. The overall benefit/risk balance is acceptable for further clinical development of SAR442168.

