9.4.2 Safety analyses

All safety analyses will be performed on the Safety Population.

Table 10 - Safety analyses

Endpoint	Statistical analysis methods
Adverse events - AEs, SAEs	Overall summaries of incidence using descriptive statistics.
Clinical laboratory tests - PCSAs	Overall summaries of incidence using descriptive statistics, by visit.
Safety findings on MRI	Overall summaries using descriptive statistics, by visit.
ECG	Overall summaries using descriptive statistics by visit for parameters.
Vital signs	Overall summaries using descriptive statistics by visit for parameters.

Abbreviations: AE: adverse event; ECG: electrocardiogram; MRI: magnetic resonance imaging; PCSA: potentially clinically significant abnormalities; SAE: serious adverse event.

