2.1.4 Safety endpoints

The safety analyses will be based on the reported AEs, including safety findings on MRI, and other safety information, such as clinical laboratory, ECG, vital signs, and C-SSRS data collected in LTS16004.

Magnetic resonance imaging scans should be reviewed locally for any non-MS pathology. In case of such findings, the relevant information needs to be provided to the Investigator for appropriate safety reporting and to ensure the appropriate management of the participant's identified safety finding. When available, a diagnosis of pathology as a cause of such MRI findings or the findings themselves will be reported as an AE until the diagnosis is clear.

MS relapses are exempt from being reported as AE/SAE unless, in the judgment of the Investigator, it is unusually severe or medically unexpected. MS relapses are collected on the eCRF and analyzed as part of the efficacy analyses.

Observation periods

In general, there should be no pretreatment AEs in the LTS16004 study since participants were to roll directly into LTS16004 after completing the DRI15928 study. However, in case there is a gap, the pre-treatment period for the LTS16004 study is defined as the time from signing the ICF until first IMP intake in the LTS16004 study.

The on-treatment period is from first administration of tolebrutinib in the LTS16004 study to the last administration +10 days, including both Part A and Part B treatment periods.

The post-treatment period, if applicable, is from the end of the on-treatment period to the end of the follow-up in LTS16004.

The on-study period is from signing the ICF to the end of follow-up in the LTS16004 study.

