2.4.5 Analyses of safety data

The safety of long-term tolebrutinib treatment will be presented by SAR dose group (5/60, 15/60, 30/60, and 60/60 mg) and overall. in the safety population. Selected summaries will be included for Part A only to assess for any dose related trends in adverse events. If average exposure across the dose groups is very different, exposure adjusted summaries will be considered.

General common rules

All safety analyses will be performed on the LTS16004 safety population, unless otherwise specified, using the following common rules:

- The baseline value of planned parameters for each participant is defined as the last available value before the first study drug intake in DRI15928 whether it was a planned or an unscheduled evaluation, unless otherwise specified.
- The potentially clinically significant abnormality (PCSA) values are defined as abnormal values considered medically important by the Sponsor according to predefined criteria/thresholds based on literature review and defined by the Sponsor for clinical laboratory tests, vital signs, and ECG.
- PCSA criteria will determine which participants had at least 1 PCSA during the on-treatment period, taking into account all evaluations performed, including nonscheduled or repeated evaluations. The number of all such participants will be the numerator for the PCSA percentage.
- The on-treatment PCSA denominator by dose group for a given parameter will be based on the number of participants assessed for that given parameter in the on-treatment period by dose group on the safety population.
- For quantitative safety parameters based on central laboratory/reading measurements, descriptive statistics will be used to summarize results and change from baseline values by visit and dose group.
- All values including unscheduled measurements will be assigned to the appropriate safety analysis visit window. In the presence of multiple measurements of the same test in the same window, the one closest to the targeted visit date will be used for the by-visit summaries.
- The analysis of the safety variables will be descriptive; no systematic testing is planned.

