2.4.5.3 Other Safety

2.4.5.3.1 Analyses of laboratory, vital signs and ECG variables

The summary statistics (including number, mean, median, Q1, Q3, standard deviation, minimum and maximum) of all laboratory values (central laboratory values and changes from baseline), vital signs, and ECG variables will be calculated for each visit or study assessment (baseline, each post-baseline time point) by tolebrutinib dose group and overall. Mean changes from baseline with the corresponding standard error may be plotted over time on treatment by tolebrutinib dose group for selected parameters.

The incidence of PCSAs at any time during the TEAE period will be summarized by (biological function for laboratory data) dose group and overall, whatever the baseline level and/or according to the following baseline status categories:

- Normal/missing.
- Abnormal according to PCSA criterion or criteria.

For laboratory parameters for which no PCSA criteria are defined, similar table(s) using the normal range will be provided.

Centralized data will be used preferentially to local measures when several measurements are performed on the same date and at the same time for a given laboratory test.

Potential drug-induced liver injury

The liver function tests, namely AST, ALT, alkaline phosphatase, and total bilirubin will be used to assess possible drug-induced liver toxicity.

In addition to the PCSA summaries, a graph of the distribution of peak values of ALT versus peak values of total bilirubin will be presented on a logarithmic scale. The graph will be divided into 4 quadrants with a vertical line corresponding to $3 \times \text{ULN}$ for ALT and a horizontal line corresponding to $2 \times \text{ULN}$ for total bilirubin.

A listing of all liver function values will be provided for any participant with a treatment emergent $\text{ALT} > 3 \times \text{ULN}$ and/or $\text{AST} > 3 \times \text{ULN}$ with bilirubin $> 2 \times \text{ULN}$ including the timing in terms of days on IMP.

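### The SAP replaces the protocol's by-visit incidence of laboratory PCSAs with a single any-time percentage over Parts A and B, without recording the change

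*SAP*

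**What the plan says.** **Protocol.** PCSAs in laboratory tests are one component of the primary endpoint (section 3, Table 6), beside adverse events, serious adverse events, MRI safety findings, ECG and vital signs. For the laboratory PCSA row, Table 10 in section 9.4.2 gives the method as "Overall summaries of incidence using descriptive statistics, by visit". The adverse event row above it asks for incidence with no visit breakdown. The synopsis describes the primary analysis as "summarizing incidence of adverse events (Aes), serious adverse events (SAEs), and clinically significant abnormalities (PCSAs) for clinical laboratory tests", and there the visit wording comes only after the later clause on MRI, ECG and vital signs.

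**SAP.** Section 2.4.5 defines the numerator: "PCSA criteria will determine which participants had at least 1 PCSA during the on-treatment period, taking into account all evaluations performed", including nonscheduled and repeated ones. Section 2.4.5.3.1 then states the display: "The incidence of PCSAs at any time during the TEAE period will be summarized by" dose group, overall and baseline status. Section 2.1.4 sets the period: "The on-treatment period is from first administration of tolebrutinib in the LTS16004 study to the last administration +10 days", with both parts included.

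No PCSA table by visit or by period is planned. SAP 1.5 (protocol changes bearing on the statistics) and SAP 1.6 (changes made in the SAP) contain no entry on this.

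**The concern.** The protocol promises a count of participants with a laboratory PCSA at each visit. The SAP delivers one ever/never percentage per dose group over a period that can reach 60 four-week months. Three things follow.

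- A reader cannot see when abnormalities occurred, or how many participants were tested at the time.
- The percentage accumulates with follow-up, so it depends partly on how long participants stayed and how often they were tested.
- Under the labels 5/60, 15/60 and 30/60, an abnormality on the Part A dose and one on 60 mg in Part B are counted alike. The Part A-only tables (starred items in SAP 2.4.5.1) are adverse event and AESI summaries, not laboratory PCSAs.

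Protocol section 2.3 lists cytopenia, including thrombocytopenia, and liver enzyme elevation among the risks. These are laboratory findings for which a count over time is informative.

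**Working it through.** The documents give no PCSA rate, so there is no figure of the plan's to reproduce.

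**1. Length of the period.** A study month is 28 days (protocol 1.3). 60 × 28 = 1680 days, which matches the Month 60 target in SAP Table 2; 1680 / 7 = 240 weeks.

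**2. Scheduled hematology and biochemistry after Day 1, on treatment** (protocol Tables 1 to 3).
- Year 1: Months 1, 3, 6, 9, 12 = 5
- Years 2 to 4: Months 15, 18, 21, 24, 27, 30, 33, 36, 42, 48 = 10
- Year 5: Months 54, 60 = 2
- Total 5 + 10 + 2 = 17. The local six-week repeats in Year 1 (Table 1, footnote f) add 3, or 4 if one after Month 12 is counted, giving 20 or 21.

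**3. How the any-time percentage grows with tests.** The chance per test, p, is an assumption, shown at 0.5%, 1% and 2%. With k independent tests, P(at least one) = 1 − (1 − p)^k. To allow abnormalities to cluster within participants, a beta-binomial with mean p and assumed correlation ρ is used: a = p(1/ρ − 1), b = (1 − p)(1/ρ − 1), and P(at least one) = 1 − Γ(b + k)Γ(a + b) / [Γ(b)Γ(a + b + k)].

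| ρ | 5 tests (p = 0.5 / 1 / 2%) | 17 tests | 21 tests | Ratio 17 to 5 at p = 1% |
|---|---|---|---|---|
| 0 | 2.5 / 4.9 / 9.6% | 8.2 / 15.7 / 29.1% | 10.0 / 19.0 / 34.6% | 15.7 / 4.9 = 3.2 |
| 0.1 | 2.1 / 4.1 / 8.0% | 4.8 / 9.4 / 18.0% | 5.5 / 10.6 / 20.2% | 9.4 / 4.1 = 2.3 |
| 0.3 | 1.5 / 3.0 / 5.9% | 2.7 / 5.3 / 10.3% | 2.9 / 5.7 / 11.1% | 5.3 / 3.0 = 1.8 |
| 0.5 | 1.1 / 2.3 / 4.5% | 1.7 / 3.4 / 6.7% | 1.8 / 3.6 / 7.1% | 3.4 / 2.3 = 1.5 |

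**4. What one percentage hides.** Take 126 participants (SAP 1.3), all tested at every visit, with independent tests. A constant 1% per test over 17 tests gives 15.7% ever, and 126 × 0.01 = 1.3 participants expected at each visit. Now confine the risk to two visits and keep the same 15.7%: the chance per test is 1 − (1 − 0.157)^(1/2) = 0.082, or 126 × 0.082 = 10.3 participants at each of those two visits and none elsewhere. The any-time table is the same in both cases; a by-visit table separates them.

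**5. What the other SAP outputs show.**

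| Output | What it gives | What it lacks |
|---|---|---|
| By-visit summaries of values (2.4.5.3.1) | Mean, median, quartiles, minimum and maximum | Number of participants crossing a threshold. Laboratory values are central, so the local Year 1 repeats may be absent |
| Peak ALT against peak bilirubin plot | Joint extremes | Time |
| Liver listing | Days on study drug | Number tested. Its wording leaves open whether raised ALT without raised bilirubin qualifies |
| AESI tables and listing (2.1.4.1, 2.4.5.1) | ALT and thrombocytopenia, with tables overall and for Part A | An onset day is not promised. Platelet events need the preferred term and a ticked AESI box. Neutropenia is not an AESI |

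**6. Unscheduled tests.** SAP 2.4.5 assigns unscheduled values to analysis windows, while SAP 2.5.4 keeps them out of by-visit summaries. A value that counts as a PCSA may therefore appear in no by-visit laboratory table.

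**The case against.** The best defence is that laboratory PCSA incidence is delivered, and in a sensitive form: it counts every evaluation, including repeats. Protocol 9.4 calls itself a summary, the synopsis does not clearly attach visits to PCSAs, and the study is descriptive with no hypothesis. All of that is correct. It does not remove the explicit wording of Table 10 or the missing entry in SAP 1.5 or 1.6.

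Four stronger readings are tempting, and the documents do not support them.

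- *That the primary safety analysis is not delivered.* Laboratory PCSAs are one component of several, and one tabulation of them is absent.
- *That all timing is lost.* A marked ALT rise can move a visit's maximum and a platelet fall its minimum, and the liver listing gives days on drug. What is missing is a count over time.
- *That the percentage mostly reflects the number of tests.* That needs an invented per-test risk and independence, and the growth shrinks quickly with clustering. Dose groups share one schedule, no planned table compares early stoppers with completers, and the SAP will consider exposure adjustment if average exposure differs greatly between groups. That last provision is conditional and does not address differing follow-up within a group.
- *That the table would hide the known liver signal.* Protocol 2.3 says "The reported events occurred in Months 1 to 3 after the start of the IMP", but this describes the Phase 3 trials. Participants here had already completed DRI15928, with 12 weeks of active drug (12 / 4 = 3 study months), and SAP Table 2 counts from first intake in LTS16004. Its Months 1 to 3 are therefore roughly exposure Months 4 to 6.

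It is also fair to say that Table 2 windows alone would not isolate the change to 60 mg, because protocol Table 1 (footnote n) allows the switch at an unscheduled visit. That is a reason to add a second time axis, not to omit the table.

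**Conclusion.** The point holds as a departure from the protocol that the SAP does not record, with a moderate consequence for interpretation. The mismatch rests on the text alone and needs no assumption.

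The any-time percentage rises with follow-up. At an assumed 1% per test, the rise from 5 to 17 tests lies between 1.5-fold (correlation 0.5) and 3.2-fold (independence). The direction is certain; the size is illustrative, because neither the PCSA rate nor the correlation is in the documents.

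The pooling of Part A doses with later 60 mg exposure is the more important reason to act, since three of the four dose groups change dose during the study. The gap is widest for platelets and neutrophils, whose PCSA onset is shown nowhere in the planned output.

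**What to change.** Keep the any-time table and add to SAP 2.4.5.3.1:

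- For each laboratory PCSA (at least ALT, AST, bilirubin, platelets and neutrophils), by dose group and overall, n/N participants with a PCSA in each Table 2 window, where N is the number tested in that window.
- In the same table, the number with a first PCSA in that window.
- A statement that all on-treatment evaluations count, local and unscheduled ones included, with SAP 2.4.5 and 2.5.4 reconciled to match.
- The PCSA table for Part A by dose (5, 15, 30, 60 mg), and a display by time since the start of 60 mg, stating the start date used for the 60/60 group.

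Record the addition in SAP 1.6. If the sponsor prefers not to produce the by-visit table, SAP 1.6 should record and justify the departure from protocol Table 10.

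The cost is a few SAP lines and one or two extra tables, using data already collected and mostly existing windows. Small counts per window will make some cells sparse, which is acceptable in a descriptive table.

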10.2 APPENDIX 2: CLINICAL LABORATORY TESTS

The tests detailed in [Table 11](#) will be performed by the central or local laboratory (as mentioned in the table).

Additional tests may be performed at any time during the study as determined necessary by the Investigator or required by local regulations.

Table 11 - Protocol-required laboratory assessments

Laboratory assessments	Parameters			
Hematology (central)	Platelet count	RBC indices:	White blood cell (WBC) count with differential:	
	Red blood cell (RBC) count	MCV	Neutrophils	
	Hemoglobin	MCH	Lymphocytes	
	Hematocrit	% reticulocytes	Monocytes	
			Eosinophils	
			Basophils	
Clinical chemistry (central) ^a	Blood urea nitrogen (BUN)	Potassium	Aspartate aminotransferase (AST)/ serum glutamic-oxaloacetic transaminase (SGOT)	Total and direct bilirubin
	Creatinine	Sodium	Alanine aminotransferase (ALT)/ serum glutamic-pyruvic transaminase (SGPT)	Total protein
	Glucose	Calcium	Alkaline phosphatase	Serum FSH Serum human chorionic gonadotropin (HCG) pregnancy test
	Creatine phosphokinase (CPK) ^b			
Routine urinalysis (central)	
 • Specific gravity • pH, glucose, protein, blood, ketones, bilirubin, urobilinogen, nitrite, leukocyte esterase by dipstick • Microscopic examination (if blood or protein) 			
Other screening tests (local)	
 • Urine human chorionic gonadotropin (HCG) pregnancy test (as needed for women of childbearing potential)^c 			
The results of each locally done test must be entered into the eCRF.				

NOTES:

a Details of liver chemistry stopping criteria and required actions and follow-up assessments after observations of ALT $>3 \times$ ULN are given in Appendix 6, [Section 10.6](#). Clinical laboratory findings of ALT $\geq 3 \times$ upper limit of normal (ULN) and bilirubin $\geq 2 \times$ ULN ($>35\%$ direct bilirubin) or ALT $\geq 3 \times$ ULN and international normalized ratio (INR) >1.5 , if INR measured that may suggest severe liver injury must be reported as an SAE.

b Required in Year 1 only

c Local urine testing is sufficient unless a pregnancy is detected or the urine test is inconclusive and a serum test needs to be used for verification, or only serum testing is required by local regulation or IRB/IEC.

Investigators must document their review of each laboratory safety report.

10.3 APPENDIX 3: ADVERSE EVENTS: DEFINITIONS AND PROCEDURES FOR RECORDING, EVALUATING, FOLLOW-UP, AND REPORTING

DEFINITION OF AE

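### Liver PCSA counts and the liver listing's ALT/AST trigger stop 10 days after last dose, before the protocol's off-drug follow-up, and the SAP's liver analysis leaves out INR

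*SAP*

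**What the plan says.** **Observation period.** SAP 2.1.4: "The on-treatment period is from first administration of tolebrutinib in the LTS16004 study to the last administration +10 days". SAP 2.1.4.1 ties treatment-emergent events to this period.

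**PCSAs.** SAP 2.4.5: "PCSA criteria will determine which participants had at least 1 PCSA during the on-treatment period". SAP 2.4.5.3.1 repeats the limit by referring to the TEAE period.

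**Liver section.** SAP 2.4.5.3.1: "The liver function tests, namely AST, ALT, alkaline phosphatase, and total bilirubin will be used to assess possible drug-induced liver toxicity". It plans a plot of peak ALT against peak total bilirubin with lines at 3×ULN and 2×ULN, and gives no period for the peaks. It then adds: "A listing of all liver function values will be provided for any participant with a treatment emergent" ALT above 3×ULN and/or AST above 3×ULN "with bilirubin $> 2 \times \text{ULN}$ including the timing in terms of days on IMP".

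**Protocol definition.** Table 11 note a (section 10.2) names two findings: ALT ≥3×ULN with bilirubin ≥2×ULN (more than 35% direct), or ALT ≥3×ULN with INR above 1.5, "if INR measured that may suggest severe liver injury must be reported as an SAE".

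**Protocol follow-up.** Section 8.2.4 has clinically significant laboratory abnormalities arising during the study or within 4 weeks of last dose repeated until they settle. The schedule of activities sets a follow-up visit 4 to 6 weeks after premature end of treatment. For completers who do not enter the Phase 3 extension it sets one 8 weeks after last dose, with biochemistry marked. Section 7.1.1 keeps participants who stop for good under study procedures to the scheduled study completion.

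**The concern.** Long-term safety is the primary objective and laboratory PCSAs are part of the primary endpoint (protocol section 3). Protocol 2.3 names drug-induced liver injury as the identified risk, and section 10.1.5 sets up a hepatology committee for it. Liver enzyme rises are also among the events that lead to stopping the drug (protocol 7.1.2). If such a stop becomes permanent, the event itself starts the 10-day clock, and values that first cross a threshold later fall outside the laboratory-based count. Laboratory case finding is the part of the safety analysis that does not depend on an investigator filling in a form, and it is the part that closes early.

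**Working it through.** The documents give no figure to reproduce. Two checks were made.

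**1. Timing.** Inputs: cut-off at last dose +10 days (SAP 2.1.4); follow-up times and retest rule (protocol 1.3 and 8.2.4); analysis windows with 1 month = 28 days (SAP Table 2). End of treatment is taken as the day of last dose.

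- Retest rule: 4 weeks = 28 days. 28 − 10 = 18 of those days lie past the cut-off.
- Premature-stop follow-up at day +28 to +42: 28 − 10 = 18 and 42 − 10 = 32 days past it.
- Follow-up after Month 60 at day +56: 56 − 10 = 46 days past it. If the ±10-day visit window applies, 46 − 10 = 36 to 66 − 10 = 56 days.
- Month 60 target: 60 × 28 = day 1680. The last window closes on day 1708. The 8-week visit falls near 1680 + 56 = day 1736, or at the earliest 1670 + 46 = day 1716. Both are beyond 1708, so this sample enters no by-visit table either.

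Unscheduled retests fare no better under SAP 2.5.4, which uses them only for baseline and PCSAs. SAP 2.4.5 says instead that unscheduled values are assigned to visit windows; the two sections need reconciling.

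Consequence by test:

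- A first ALT or AST crossing after day +10 is in neither the PCSA counts nor the listing trigger.
- A first bilirubin crossing after day +10 is outside the PCSA counts. Whether it can complete the listing trigger for an on-treatment ALT or AST rise is not stated, because treatment-emergent is attached to the enzymes only.
- A temporary interruption followed by restart stays inside the window, since the period runs to the final dose.

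**2. Who is selected.** The SAP wording has two readings. Reading A: (ALT >3 or AST >3) with bilirubin >2. Reading B: ALT >3 alone, or AST >3 with bilirubin >2. Illustrative on-treatment profiles, as multiples of ULN except INR:

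| Profile | Protocol note a | SAP, reading A | SAP, reading B |
|---|---|---|---|
| ALT 5, bilirubin 1, INR 1.8 | yes | no | yes |
| ALT 1, AST 5, bilirubin 3 | no | yes | yes |
| ALT 5, bilirubin 3, 20% direct, INR 1.0 | no | yes | yes |

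Apart from values exactly on a cut-off, the only profile that note a flags and reading A misses is ALT >3 with INR >1.5 and bilirubin not above 2×ULN. Under reading B nothing is missed except at equality. Under either reading, the rules overlap and neither contains the other.

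**The case against.** **Other listings catch these cases.** The SAP lists all SAEs and all AESIs whatever their treatment-emergent status, and lists and summarizes post-treatment AEs (2.4.5.1). Findings that meet note a must be reported as SAEs, ALT above 3×ULN is an AESI (protocol 8.3.1), and three hepatologists review potential cases. This stands: a reader might infer that post-stop injury vanishes from the report, and it does not. But each listing starts with an investigator report, and the ALT AESI is selected by a form category and a ticked box (SAP Table 1). Nothing says these listings carry peak ALT, bilirubin or INR.

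**A participant once selected is fully shown.** The listing gives all liver values with timing, so later peaks in someone already selected do appear, and the peak plot has no stated cut-off. This also stands. The gap concerns first crossings, and the plot's period needs stating rather than correcting.

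**The value that prompts stopping is usually on treatment.** If it meets a PCSA threshold, that participant is already counted. What can be lost is a first crossing of a higher ALT category or of a bilirubin threshold. The numeric PCSA limits are not in the documents, so the extent cannot be shown.

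**Ten days has a rationale.** Protocol 8.4 expects activity to last at least 9 days. That supports keeping the on-treatment count; it does not argue against a second count beside it.

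**Few cases are likely.** Reported injuries arose in Months 1 to 3, and entrants had already had 12 weeks of active treatment. The move to 60 mg in Part B raises the dose for three of the four groups, so this argument is weaker than it looks.

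**INR is not a scheduled test.** It is not in the Table 11 panel and counts only where measured. That limits the gap but does not close it.

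**Conclusion.** The concern holds in a limited form. Liver PCSA incidence and the listing's ALT/AST trigger end at day +10, which is 18 to 46 days before the follow-up visits. A first ALT or AST crossing in that interval is left to investigator reporting, and a first bilirubin crossing is lost to the PCSA counts. INR is unused, and under reading A an ALT-plus-INR case without raised bilirubin is not selected.

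The number affected cannot be derived and may be zero. For scale, one participant among the 126 enrolled (SAP 1.3) is 1/126 = 0.8%. In an average dose group of 126/4 = 31.5, assuming groups of about equal size, it is 1/31.5 = 3.2%.

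Three stronger readings are not supported:

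- That the SAP rule is narrower than the protocol's: it adds AST and omits the direct-bilirubin condition.
- That strict rather than inclusive inequalities lose cases: they differ only at exact equality, and the protocol's own ALT AESI is strict.
- That some percentage of cases is missed: the documents hold no data on the lag between stopping and the peak, so any such figure would rest on an invented distribution.

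The ALT flow chart in Appendix 6 is a figure not available in the text reviewed; nothing here relies on its content.

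**What to change.** In SAP 2.4.5 and 2.4.5.3.1, before database lock:

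1. Base the ALT–bilirubin peak plot and the liver listing, including its trigger, on all values from first LTS16004 dose to end of follow-up. Flag values more than 10 days after last dose. Show liver PCSA incidence for this period beside the on-treatment count, with participants assessed in each period as the denominator.
2. Add ALT ≥3×ULN with INR above 1.5, where INR was measured, as a further listing trigger, and print INR in the listing.
3. Write out the and/or logic with brackets, without removing any ALT >3×ULN case that already qualifies under reading B.

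The cost is SAP wording and a small programming change on data the protocol already collects; no visit, test or patient-management rule changes. The one drawback is that some off-drug values with other causes will be included, and the flag lets the reader separate them.
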